5.1.3 Presentation of results

Adverse events occurring in ITP0 will only be listed. AEs will be tabulated by AChR-Ab status and overall and within AChR-Ab status, by cycle and overall.

An overview table will show the number and percentage of patients with at least one event, the number of events and event rates per patient years of follow-up for the following:

- TEAEs
- Serious TEAEs
- Grade ≥ 3 TEAEs
- TEAEs of special interest
- IRR events
- Fatal TEAEs
- Treatment-related TEAEs according to the Principle Investigator
- Procedures-related TEAEs according to the Principle Investigator
- Serious treatment-related TEAEs
- TEAEs for which the study drug was discontinued

Summary tables by MedDRA system organ class and preferred term will show the number and percentage of patients with at least one event. The table of TEAEs will additionally show the number of events.

	
Statistical Analysis Plan
	

ARGX-113-1705
	
Final Analysis
	
Final 1.0 of 20SEP2022

Separate tables will be prepared for the following TEAEs:

- Serious TEAEs
- Non-serious TEAEs
- Grade ≥ 3 TEAEs
- IRR events
- Treatment-related TEAEs
- Procedures-related TEAEs
- Serious treatment-related TEAEs
- Serious IRR events
- TEAEs for which the study drug was discontinued

All AEs, including pre-treatment events will be listed.

COVID related events (events with preferred term COVID-19, COVID-19 pneumonia, suspected COVID-19 and coronavirus infection) will be listed. This listing will include all collected AE information and additionally the cycle, onset since first efgartigimod dose, onset since last efgartigimod dose before AE onset, last total IgG before AE onset, the last percent change in total IgG before AE onset and the time when that reported total IgG was taken compared to AE onset.

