6. TRIAL TREATMENT

6.1. Treatment Administered

Only patients who need (re-)treatment with efgartigimod, provided they are eligible (see Section 4.1 for the criteria for [re-]treatment), will be treated with efgartigimod.

Efgartigimod will be administered weekly for 3 weeks (4 infusions) as an IV infusion (total volume of 125 mL and a dose of 10 mg/kg of body weight) at visits 1, 2, 3 and 4 of each Treatment Period. A variation of $\pm 10\%$ of the amount, as planned per protocol, of efgartigimod administered to the patient will not be considered an overdose/underdose. In case of a significant ($>10\%$) change in body weight, the dose will be recalculated.

Although efgartigimod was administered over a period of 2 hours in all the other clinical trials conducted so far, in this trial, for patient's convenience and because no safety concerns are anticipated based on observations in the other trials, efgartigimod will be administered over a period of 1 hour. Please refer also to the IB, Section 6.3.

Details on infusion rate and time will be given in the IMP management manual (pharmacy manual).

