1.2 STUDY DESIGN

This is a phase 3 multicentre, single arm, Open-Label Extension (OLE), Follow-on study of ARGX-113-1704 assessing the long-term safety and tolerability of (intravenous) ARGX-113 in adults with generalized myasthenia gravis (gMG).

	Statistical Analysis Plan	
ARGX-113-1705	Final Analysis	Final 1.0 of 20SEP2022

At the End of Study visit of trial ARGX-113-1704, eligible patients were offered the option to roll over into this trial. Hence, the maximum number of patients in this trial is the number of patients who participated in trial ARGX-113-1704.

Within trial ARGX-113-1705, a variable number of Treatment periods (i.e. 4 weekly infusions of ARGX-113 infused over a period of 3 weeks) were administered to eligible patients on an “as needed basis” on top of their SoC in Treatment Periods.

The anticipated study duration was a maximum of 3 year after entry into the OLE. After the first year (part A), the number and frequency of assessments decreased for the remaining time in the study (part B). During part B, patients had the opportunity to enter study ARGX-113-2002 to be treated with subcutaneous ARGX-113 and PH20.

The schedule of assessments is in appendix [9.2](#).

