2.2 PHASES, PERIODS AND TIME POINTS

2.2.1 *Phases and periods*

All events and assessments will be allocated to phases and periods (see Table 1). A patient can start in 1705 in an inter-treatment period or in a cycle, depending on the patient status regarding the need for (re-)treatment upon roll-over. Each period following ITPO coincides with a cycle and includes the 4 administrations of efgartigimod and the inter-treatment period (ITP) visits. The length of the ITP is patient specific and can differ between the different periods. The number of patients may decline for each subsequent cycle.

	Statistical Analysis Plan	
ARGX-113-1705	Final Analysis	Final 1.0 of 20SEP2022

Table 1: phase/period definition

Phase	Period	Start	End
Treatment	ITP0	Earliest of (date of signing the informed consent form (ICF) and date of roll-over), with 00:00 added as time part.	First administration date/time in cycle 1 – 1 minute
	Cycle 1	First administration date/time in cycle 1	First administration date/time in next cycle – 1 minute or if last cycle: date of last contact, with 23:59 added as time part
	Cycle n	First administration date/time in cycle n	First administration date/time in next cycle – 1 minute or if last cycle: date of last contact, with 23:59 added as time part
	Cycle x	First administration date/time in cycle x	Date of last contact, with 23:59 added as time part

AEs and concomitant medications will be allocated to phases and periods as described in sections 5.1.2 and 3.5.2 respectively. All other assessments will be allocated to phases and periods based on the assessment date/time.

In case of (partially) missing date/time fields disabling allocation or date(time) equal to dosing date(time), information from visit label and protocol schedule of assessments (SoA) will be used to allocate to the correct period. If this is not possible, assessments will be allocated to the first possible cycle (not ITP0) unless the available parts of the assessments start or stop date/time provide evidence the assessments did not occur during that period.

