3.6.2 Derivation rules

The following parameters will be derived:

- Number of administrations: number and percentage of patients who had 1, 2, 3 etc.... administrations per cycle and overall
- Actual dose (mg/kg) per administration per cycle, using categories <9mg/kg, 9-11 mg/kg, >11mg/kg.
- Treatment compliance per cycle defined as (number of doses received/4)*100%
- The actual dose in mg/kg will be calculated as =

$$\left(\frac{\text{actual volume extracted from vials (mL)} * 20 \text{ (mg/mL)}}{\text{actual volume extracted from vials (mL)} + \text{actual volume of NaCl solution added to IV bag (mL)}} \right) * \left(\frac{\text{actual volume infused (mL)}}{\text{last available patient weight (kg) before or at day of dosing}} \right)$$
- Note: As per protocol a variation of $\pm 10\%$ of the amount of 10 mg/kg, will not be considered an overdose/under dose.

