5. SAFETY ANALYSES

5.1 ADVERSE EVENTS

5.1.1 *Available data*

Adverse events (AEs) are coded into system organ classes and preferred terms using the MedDRA version 24.1 (SEP2021). AEs were graded using the National Cancer Institute (NCI) Common Terminology Criteria for Adverse Events (CTCAE) version 5.0. For each AE, start and stop date/times are collected as well as severity, a seriousness flag, treatment relatedness, relatedness to procedures, action taken towards the study drug and outcome.

5.1.2 *Derivation rules*

Based on their start date/time, AEs will be allocated to the analysis period during which they started. Each AE will therefore be reported in only one period. Periods are defined in section 2.2.1. In case the AE start date/time is incomplete or missing and the AE could consequently be allocated to more than one period, AE will be allocated to the first possible cycle unless the available parts of the AE start or stop date/time provide evidence the assessments did not occur during that period.

Event rates per patient years of follow-up (PYFU) will be defined as the number of events divided by the sum of follow-up time (i.e. duration of treatment phase) of all participants per treatment expressed in years.

A death case is defined as an AE with outcome ‘fatal’.

Adverse events of special interest will be defined using MedDRA SOC ‘Infections and infestations’.

Infusion-related reactions (IRR) will be defined as all AEs with a MedDRA preferred terms that are listed in either:

- MedDRA Hypersensitivity SMQ broad selection
- MedDRA Anaphylactic reaction SMQ broad selection
- MedDRA extravasation events (injections, infusions and implants) SMQ broad selection, excluding implants

AND occurring within 48 hours of an infusion, or within 2 days in case no AE start time is available.

An AE for which the study drug was discontinued is defined as an AE with action taken ‘drug withdrawn’.

Treatment-relatedness will be dichotomised as follows in tables:

- Treatment-related: related, probably related, possibly related or missing
- Not treatment-related: not related, unlikely related, not applicable

	
Statistical Analysis Plan
	

ARGX-113-1705
	
Final Analysis
	
Final 1.0 of 20SEP2022

AE onset and duration will be calculated as follows when start and stop dates are fully known

- AE onset day (vs. first administration)

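### The infusion-related reaction rate per patient-year mixes risk per infusion with re-treatment frequency; a rate per 100 infusions should be added beside it.

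*SAP*

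**What the plan says.** SAP 5.1.2 defines an IRR as an adverse event whose preferred term falls in one of three MedDRA queries, "AND occurring within 48 hours of an infusion, or within 2 days in case no AE start time is available". The same section defines the event rate as "the number of events divided by the sum of follow-up time (i.e. duration of treatment phase) of all participants per treatment", expressed in years. SAP 5.1.3 puts IRR events in the overview list, which shows patients with an event (number and percentage), "the number of events and event rates per patient years of follow-up for the following". The results are split by AChR-Ab status and by cycle.

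Dosing is irregular by design. SAP 1.2 describes "a variable number of Treatment periods (i.e. 4 weekly infusions of ARGX-113 infused over a period of 3 weeks", given as needed. On the gap after each course, SAP 2.2.1 says: "The length of the ITP is patient specific and can differ between the different periods". The treatment phase, which is the follow-up clock, starts with ITP0 (the stretch before the first course in this trial), at "Earliest of (date of signing the informed consent form (ICF) and date of roll-over". SAP 5.1.3 keeps ITP0 events out of the tables; they appear in listings only.

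Infusion counts exist elsewhere. SAP 3.6.2 derives the "number and percentage of patients who had 1, 2, 3 etc.... administrations per cycle and overall", reported in Table 14.1.2.6. No table relates IRRs to the number of infusions.

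**The concern.** The numerator can grow only in short windows after infusions, while the denominator grows every day. How much window time a patient-year contains depends on how often the patient needed re-treatment, which is a feature of the disease course. Two groups with the same risk at each infusion can show different IRR rates, and a group with a higher risk per infusion can show the lower rate.

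Tolerability is part of the primary objective, in AChR-Ab seropositive patients. Results are split by AChR-Ab status, by cycle and by treatment received in trial 1704, and re-treatment frequency may differ along any of these. Infusion tolerability also has a specific interest here. Protocol 6.1 states "Although efgartigimod was administered over a period of 2 hours in all the other clinical trials conducted so far", whereas this trial infuses over 1 hour. The natural unit for that interest is the infusion.

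**Working it through.** The documents state no IRR rate and no IRR risk per infusion, so there is no figure to reproduce. Protocol 1.4 says only that IRR frequency was low. Let *p* be the expected number of IRRs per infusion. Values of 0.5%, 1% and 2% are assumptions for illustration.

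**Inputs from the documents**
- Four planned infusions per treatment period (SAP 1.2).
- About 2 at-risk days per infusion (SAP 5.1.2), so 4 × 2 = 8 days per full course.
- One to six treatment periods in the Part A year. This is the range used for the blood-volume estimate in Protocol 7.2.2.
- At least 4 weeks between visit 4 and the next visit 1 in Part B (Protocol 4.1), so the shortest cycle is 21 + 28 = 49 days.

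**Overall rate** = *p* × infusions per year. **At-risk share** = 2 × infusions per year / 365.25.

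| Re-treatment | Infusions per year | At-risk share | *p* = 0.5% | *p* = 1% | *p* = 2% |
|---|---|---|---|---|---|
| 1 period | 4 | 2.2% | 0.02 | 0.04 | 0.08 |
| 3 periods | 12 | 6.6% | 0.06 | 0.12 | 0.24 |
| 6 periods | 24 | 13.1% | 0.12 | 0.24 | 0.48 |
| 49-day cycles | 4 × 365.25 / 49 = 29.8 | 16.3% | 0.15 | 0.30 | 0.60 |

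The ratios do not depend on *p*: 24 / 4 = 6, and 29.8 / 4 = 7.5. Per 100 infusions, every row gives 0.5, 1.0 or 2.0.

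**Reversal.** With *p* = 2% and one period a year the rate is 0.02 × 4 = 0.08. With *p* = 1% and six periods it is 0.01 × 24 = 0.24. The group with half the risk per infusion shows three times the rate.

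**ITP0.** Take three periods at *p* = 1% over 365 days, plus an ITP0 of 0, 90 or 180 days. Then 0.12 / (365/365.25), 0.12 / (455/365.25) and 0.12 / (545/365.25) give 0.12, 0.096 and 0.080.

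**By cycle.** SAP 5.1.2 defines no follow-up time per cycle. If cycle duration were used, four infusions at *p* = 1% would give 0.04 / (51/365.25) = 0.29 per patient-year for a 51-day cycle and 0.04 for a 365-day cycle.

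**Percentages in the same table.** Assume independent infusions with at most one IRR each, at *p* = 1%. The chance of at least one IRR in a full cycle is 1 − 0.99⁴ = 3.9%, whatever the cycle length. A patient who received one infusion in the cycle has 1.0%. Over the whole trial, 4 infusions give 3.9% and 24 give 1 − 0.99²⁴ = 21.4%.

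**The case against.** The strongest reply is that the plan already contains most of what is needed. The overview table also gives event counts and patient percentages by cycle, and SAP 2.4.1 sets the percentage denominator as patients per treatment and cycle. A cycle has four planned infusions, so that percentage is close to a measure per four infusions and is unaffected by the length of the gap. Infusion counts are in Table 14.1.2.6, so a crude overall figure can be worked out by hand. The per-year rate also answers a fair question: how many IRRs to expect in a year of as-needed treatment. Everything here is descriptive, with no test or threshold attached.

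Much of this stands. A reader might infer that the rate says nothing about tolerability, and that would be wrong: doubling the risk per infusion doubles the rate. A reader might also infer that the plan has no infusion-linked measure, or that the per-year rate should be deleted. The by-cycle percentages and the burden interpretation do not support either.

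What remains is narrower. The by-cycle percentage counts a patient once however many IRRs occur, and ignores missed doses, although Protocol 4.4.2 keeps patients who miss one to three infusions in the trial. The overall percentage rises with infusions received. The SAP table list does not split Table 14.1.2.6 by AChR-Ab status, so the hand calculation is not directly available for the seropositive population of the primary objective.

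**Conclusion.** The point holds as a presentation weakness in one row of one table. The IRR rate per patient-year is risk per infusion multiplied by infusion frequency, and ITP0 time lowers it further. Across the re-treatment range in the protocol, equal tolerability gives a 6-fold range of rates, or 7.5-fold up to the Part B minimum spacing. These ratios assume a constant risk per infusion and full courses; the absolute rates also rest on the assumed *p*.

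Two inferences go too far. The 6- to 7.5-fold range describes individual re-treatment patterns. The table pools events and follow-up within groups, so the distortion between groups is the ratio of their mean infusions per year, and the documents do not give that. Nor would a per-infusion rate by itself show whether 1-hour infusion is tolerated as well as 2-hour infusion. The trial has a single arm with infusions planned over 1 hour, so that comparison needs data from outside it.

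The change is worth making because the better denominator is already derived. No hypothesis test or sample size is affected.

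**What to change.** In SAP 5.1.3, add IRR events per 100 infusions to Table 14.3.1.1, beside the rate per patient-year, overall, by cycle and by AChR-Ab status. Take the denominator from the administration data in SAP 3.6.2, and state that it counts infusions actually given. This also removes ITP0 from the calculation. Keep the per-year rate as a measure of IRR burden.

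If serious IRRs are wanted on the same scale, add the figure to Table 14.3.1.11. They are not in the overview list, so they have no per-year rate in Table 14.3.1.1.

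The cost is one derived row or column in a descriptive table, from data already collected.

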3. TRIAL ENDPOINTS

3.1. Primary Endpoint

Incidence and severity of AEs, serious adverse events (SAEs), vital signs, ECG and laboratory assessments over the duration of the trial in AChR-Ab seropositive patients.

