3.2. Secondary Endpoint

Incidence and severity of AEs, SAEs, vital signs, ECG and laboratory assessments over the duration of the trial in the overall population (AChR-Ab seropositive patients and AChR-Ab seronegative patients).

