All AEs observed will be graded using the National Cancer Institute (NCI) Common Terminology Criteria for Adverse Events (CTCAE) version 5.0. The NCI-CTCAE is a descriptive terminology, which can be utilized for AE reporting. A grading (severity) scale is provided for each AE term. Grade refers to the severity of the AE. If a particular AE's severity is not specifically graded by the guidance document, the investigator is to use the general NCI-CTCAE definitions of Grade 1 through Grade 5 following his or her best medical judgment. The CTCAE displays Grades 1 through 5 with unique clinical descriptions of severity for each AE based on the following general guideline:

- Grade 1: Mild; asymptomatic or mild symptoms; clinical or diagnostic observations only; intervention not indicated.
- Grade 2: Moderate; minimal, local or non-invasive intervention indicated; limiting age--appropriate instrumental activities of daily living (ADL).
- Grade 3: Severe or medically significant but not immediately life-threatening; hospitalization or prolongation of hospitalization indicated; disabling; limiting self-care ADL.

- Grade 4: Life-threatening consequences; urgent intervention indicated.
- Grade 5: Death related to AE.

Relationship

The causal relationship between efgartigimod/trial procedures and the AE has to be characterized as unrelated, unlikely, related, possible, and probable.

- Events can be classified as “unrelated” if there is not a reasonable possibility that efgartigimod caused the AE.
- An “unlikely” relationship suggests that only a remote connection exists between efgartigimod and the reported AE. Other conditions, including chronic illness, progression or expression of the disease state, or reaction to concomitant medication, appear to explain the reported AE.
- A “related” relationship suggests that the AE follows a reasonable temporal sequence from administration of efgartigimod, it follows a known or expected response pattern to efgartigimod and it cannot reasonably be explained by known characteristics of patient’s clinical state.
- A “possible” relationship suggests that the association of the AE with efgartigimod is unknown; however, the AE is not reasonably supported by other conditions.

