14.2.4.1	ADA: Number and Percentage of Patients with Anti-Drug Antibodies to Efgartigimod by Analysis Visit	SAF
14.2.4.2	ADA: Prevalence and Incidence of Anti-Drug Antibodies by Cycle and Overall	SAF
14.2.4.3	ADA: Descriptive Statistics of Anti-Drug Antibodies Titer Values by Overall ADA Subject Category	SAF
14.2.4.4	NAb: Number and Percentage of Patients with Positive NAb to Efgartigimod by Analysis Visit	SAF
14.2.4.5	NAb: Prevalence and Incidence of NAb by Cycle and Overall	SAF
14.2.4.6	NAb: Number and Percentage of NAb Positive Patients by Overall ADA Subject Category	SAF

SAFETY

ADVERSE EVENTS

14.3.1.1	Adverse Events Overview	SAF
14.3.1.2	Treatment-Emergent Adverse Events by MedDRA System Organ Class and Preferred Term	SAF
14.3.1.3	Serious Treatment-Emergent Adverse Events by MedDRA System Organ Class and Preferred Term	SAF
14.3.1.4	Non-serious Treatment-Emergent Adverse Events by MedDRA System Organ Class and Preferred Term	SAF
14.3.1.5	Grade 3 or More Treatment-Emergent Adverse Events by MedDRA System Organ Class and Preferred Term	SAF
14.3.1.6	Treatment-Related Treatment-Emergent Adverse Events by MedDRA System Organ Class and Preferred Term	SAF
14.3.1.7	Procedures-Related Treatment-Emergent Adverse Events by MedDRA System Organ Class and Preferred Term	SAF
14.3.1.8	Serious Treatment-Related Treatment-Emergent Adverse Events by MedDRA System Organ Class and Preferred Term	SAF
14.3.1.9	Treatment-Emergent Adverse Events Leading to Discontinuation of Study Drug by MedDRA System Organ Class and Preferred Term	SAF
14.3.1.10	Infusion-Related Reactions by MedDRA System Organ Class and Preferred Term	SAF
14.3.1.11	Serious Infusion-Related Reactions by MedDRA System Organ Class and Preferred Term	SAF

LABORATORY DATA

14.3.2.1	Descriptive Statistics of Laboratory Test Actual Values and Changes from Baseline	SAF
----------	---	-----

	Statistical Analysis Plan	
ARGX-113-1705	Final Analysis	Final 1.0 of 20SEP2022

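### Severity is part of the primary endpoint, but AE tables use CTCAE grade only at 3 or more, with deaths shown by outcome, so mild and moderate events are not separated

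*SAP*

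**What the plan says.** Protocol 3.1 gives the primary endpoint, in AChR-Ab seropositive patients, as "Incidence and severity of AEs, serious adverse events (SAEs), vital signs, ECG and laboratory assessments over the duration of the trial". Protocol 3.2 repeats it for the overall population. On grading, Protocol 7.2.1 says: "The CTCAE displays Grades 1 through 5 with unique clinical descriptions of severity for each AE". SAP 5.1.1 confirms that the grade is available: "For each AE, start and stop date/times are collected as well as severity".

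For display, SAP 5.1.3 plans an overview table with ten rows, one of them for grade 3 or more and one for fatal treatment-emergent AEs (TEAEs). SAP 5.1.2 defines a death by the outcome of the AE, not by its grade. For the other tables the SAP says: "Summary tables by MedDRA system organ class and preferred term will show the number and percentage of patients with at least one event". One of these is restricted by grade: "Grade 3 or More Treatment-Emergent Adverse Events by MedDRA System Organ Class and Preferred Term" (Table 14.3.1.5). AE tables are produced by AChR-Ab status and overall, and by cycle and overall. All AEs are also listed. Laboratory toxicity, by contrast, is cross-tabulated grade by grade (SAP 5.2.3).

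**The concern.** A reader of the final tables will want to know how severe the events were, and whether they became more severe as cycles accumulated. Protocol 4.2 says that safety is to be evaluated by cycle as well as over the whole trial. The CTCAE levels differ in clinical meaning. In Protocol 7.2.1, grade 1 needs no intervention and grade 2 calls for a minor one; grade 3 is severe and grade 4 is life-threatening. If infections moved from mostly grade 1 to mostly grade 2 over successive cycles, no planned AE table would need to change.

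The same gap affects statements of a kind that the protocol already makes. Its benefit-risk section (1.4) describes infusion-related reactions (IRRs) to date as mostly mild. The IRR tables planned here could neither support nor contradict such a statement for this trial, because they carry no grade.

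**Working it through.** The plan gives no figure to reproduce, so the check is a reading of every AE table in SAP 8.1 against SAP 5.1.3.

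| Table | Content | Use of grade |
|---|---|---|
| 14.3.1.1 | Overview, ten rows | One row at grade 3 or more; one row for fatal outcome |
| 14.3.1.2 | All TEAEs | None |
| 14.3.1.3, 14.3.1.4 | Serious; non-serious | None |
| 14.3.1.5 | Grade 3 or more | That threshold only |
| 14.3.1.6 to 14.3.1.8 | Treatment-related; procedures-related; serious treatment-related | None |
| 14.3.1.9 | Leading to discontinuation | None |
| 14.3.1.10, 14.3.1.11 | IRRs; serious IRRs | None |

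That is 1 + 1 + 2 + 1 + 3 + 1 + 2 = 11 tables. Two use grade, both at the same threshold.

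**What subtraction recovers.** Let A be the patients with any TEAE, G those with at least one of grade 3 or more, and F those with a fatal TEAE. G lies within A. If a fatal outcome always coincides with grade 5, F lies within G. Then, in the overview table:

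- A − G = patients whose maximum grade is 1 or 2
- G − F = patients whose maximum grade is 3 or 4
- F = patients whose maximum grade is 5

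The recoverable groups are {1, 2}, {3, 4} and {5}. By system organ class (SOC) and preferred term (PT), setting Table 14.3.1.2 against Table 14.3.1.5 gives only {1, 2} and {3, 4, 5}, because fatal events have no SOC/PT table. The overview shows event counts as well, so events can be grouped there in the same way. By SOC and PT they cannot, because event counts are confined to one table: "The table of TEAEs will additionally show the number of events".

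**Size of the unsplit group.** The documents give no expected rates, so these are assumptions for illustration: A = 80% and G = 20%. Then A − G = 80% − 20% = 60%. Within that 60%, the share whose worst event was grade 2 could lie anywhere from 0% to 60% with the same entries in the overview rows for TEAEs and for grade 3 or more. In general the unsplit share is A − G.

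**Grade 3 against grade 4.** Protocol 7.2.1 makes a life-threatening event serious by definition. There are two cases:

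1. A non-serious grade 3 event becomes life-threatening. It leaves the non-serious table and enters the serious one, so something moves.
2. A grade 3 event already serious, for example through hospitalisation, becomes grade 4. The grade 3 or more, serious and non-serious counts all stay as they were.

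**AEs of special interest.** SAP 5.1.2 defines these as the infections SOC. Infections of grade 3 or more can therefore be read from that SOC row of Table 14.3.1.5. Within grades 1 and 2 they remain unsplit.

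**Laboratory grades as a substitute.** SAP 5.2.1 says that Part B laboratory results are not in the database and that clinically significant ones are reported as AEs. The laboratory grade tables therefore cover Part A only. For Part B, the AE grade is the only severity information on laboratory abnormalities.

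**The case against.** The strongest reply is that the SAP does what the protocol's statistics section asks. Protocol 8.4.1 treats AEs as binary and requires frequency tables by cycle and overall; nothing promises a table for each grade. The trial is single-arm and descriptive, and Protocol section 8 allows further exploratory analyses. The SAP also describes severe outcomes through the serious, fatal and discontinuation displays. Every AE is listed, for at most 167 patients.

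Most of this stands. It rules out calling the SAP a departure from Protocol 8.4.1, and it shows that no data are lost. It does not close the gap. Seriousness and discontinuation are separate criteria from grade, and neither separates mild from moderate. The SAP does not state the columns of the AE listing. Even if grade is among them, the reader would have to count severity by cycle and serostatus by hand for a primary endpoint.

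The reply also raises table size. The AE tables are already split by treatment label, AChR-Ab status and cycle, so five grade levels throughout would make them unwieldy. That is fair, and the change below is limited accordingly.

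**Conclusion.** The point holds as a minor reporting gap. The severity part of the primary and secondary endpoints is tabulated for AEs at one grade threshold, plus death by outcome. Maximum grade 1 is not separated from grade 2 in any AE table. Grade 3 is not separated from grade 4 as such, and a shift between them shows only if seriousness or another tabulated attribute changes too. IRRs and treatment-related TEAEs have no grade display of their own. The illustrative 60% rests on assumed rates; the grouping that it illustrates does not.

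A reader might infer more than the documents support:

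- **That severity goes unreported, or is cut at only one point.** The fatal row in effect isolates grade 5, provided that outcome and grade agree.
- **That no table of any kind shows grades.** Laboratory toxicity is shown grade by grade for Part A.
- **That a move from grade 3 to grade 4 could never be seen.** It can move the serious and non-serious tables.
- **That severe infections are hidden.** They appear at the grade 3 threshold in the infections SOC row of Table 14.3.1.5.

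**What to change.** In SAP 5.1.3 and 8.1:

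- Add to the overview table (14.3.1.1) the number and percentage of patients by maximum CTCAE grade (1, 2, 3, 4, 5), for TEAEs and for AEs of special interest, by cycle and overall and by AChR-Ab status.
- Add one table of TEAEs by SOC and PT by maximum grade, overall across cycles only, to limit its size. Its infections SOC row then gives the result for AEs of special interest.
- Optionally, add maximum grade to the IRR table (14.3.1.10) if the report is to describe how severe IRRs were.

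The cost is one extra table and a longer overview, with sparse cells in late cycles, where SAP 2.2.1 expects patient numbers may fall. No new data are needed.
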